## A2. CONCEPTUAL MODEL: PATIENT-CENTERED ACCESS TO MENTAL HEALTH CARE

Using both theory and empirical evidence, the focus of this CDA will be to: (1) identify risk profiles associated with depression treatment engagement, to test prediction models and select patients for the proposed intervention; (2) design an eHealth intervention program using technology driven self-monitoring; and (3) conduct a formative evaluation and pilot this eHealth intervention.

First, we will identify possible patient profiles or phenotypes associated with treatment engagement. Profiles will be constructed using structured data and will be used to calculate risk scores associated with patient lack of engagement in treatment for depression (Aim 1). Guiding the development of a pre-treatment intervention (Aim 2) will be Levesque's Framework which proposes that patient's ability to **engage** is at the core of successful health care consequences (i.e., outcomes). Therefore, the focus will be on the development of an intervention that will provide patients the mechanism to initiate treatment, and then ideally remain actively engaged with their own care, which prior work has shown to increase adherence and improve treatment outcomes (e.g., Guo et. al, 2015). This will be done via active self-monitoring and specific labeling of depression symptoms, as well as via emotional and practical support. Based on this framework, the process by which behavior change about treatment is activated is by helping patients more clearly identify health care needs (i.e., via symptom monitoring) help rectify perception of needs (by providing feedback on symptoms, whether they are elevated and a provider should be contacted), helping with care seeking and reaching (i.e., sending provider contact information and sending reminders).

Formative methods will be used to evaluate and pilot this process (Aim 3) in preparation for a future efficacy/effectiveness RCT (IIR developed in year 3). Our study focuses on solidifying engagement in care for those patients whose needs have been identified by provider and have been referred for care. Focusing on this segment of the patient population with mental health care needs ensures that our sample already meets basic

[figure not shown]

Figure 1. Conceptual framework.

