##### **A4a. Aim1.**

Study/Design overview: I will conduct a secondary data analysis of EHR data. This will be a retrospective cohort study to identify patient phenotypes associated with lack of treatment engagement for depression. This aim was developed based on empirical evidence and Levesque's Framework (2013) (Figure 1), which proposes that patient level factors impact health care utilization and outcomes. Our proposed analyses will focus on data available from EHRs (observed variables). Based on this framework, patient level factors may impact the process of initiating care along a continuum of identifying health care needs, perception of needs and desire for care, health care seeking, and reaching. These factors will be captured through proxy measures available in the EHRs. For example, based on the literature reviewed in the background and my own preliminary work, identification of care needs, perception of needs, and desire for care are all a function of depression severity, gender, and ethnicity, such that higher severity, female gender, and white race tend to all be associated with higher levels of perception of needs and openness to mental health care. Specifically, for this study, we plan to use the 88,456 OEF/OIF Veterans with a Patient Health Questionnaire 9 (PHQ9)  $\geq 10$  (indicative of probable depression) randomly split into sub-samples to accommodate our goals. I plan to develop Aim 1 in two related stages. (Stage 1) First, I will develop patient profiles using conventional logistic regression analysis. In this analysis, the estimated 88,456 OEF/OIF Veterans with a PHQ9  $\geq 10$  will be randomly split into development and validation sub-cohorts. Estimates extracted from the development sub-cohort will be used to compute risk scores, with ROC analysis performed to determine a presumed optimal cut-off score. These profiles and cutoff score will be evaluated for prediction accuracy on the validation sub-cohort. (Stage 2) To evaluate the results from Stage 1, patient profiles will then be developed and validated with machine learning paradigm on the 88,456 OEF/OIF Veterans with a PHQ9  $\geq 10$ . Use of this approach is based on the fact that while various characteristics have been investigated in the past in an attempt to identify patients' likelihood to use services, we have yet to apply advanced machine learning techniques to the rich data available in the EHRs to define a profile of patients at risk to not engage in mental health care for depression. Ultimately, our goal is to identify the best fitting model in terms of prediction performance and interpretation, whether by logistic regression analysis or machine learning methods. The risk scores identified in this Aim will be utilized to recruit patients for Aims 2 and 3. While the models developed for Aim 1 will be based on "observed" variables only, there may be important "unobserved" variables we are not able to include. Methods related to this potential concern are described below in the Analysis Plan section.

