Treatment initiation	A primary or secondary stop code showing a visit in mental health (with a psychologist or psychiatrist) or primary care AND an ICD9 for depression diagnosis.

Sampling plan and data extraction and processing:

**Data source and cohort selection.** We will use data from the VA Corporate Data Warehouse (CDW), a centralized data repository which contains electronic medical records of all Veteran patients who receive care through the VHA. The patient cohort (N = 88,456) used for completion of Aim 1 includes 1) OEF/OIF Veteran patients with a PHQ9  $\geq$ , 2) who were not already in treatment for depression prior to this PHQ9 assessment, 3) were never diagnosed with bipolar, personality, psychotic, and pervasive developmental disorders to be consistent with the National Committee on Quality Assurance measure of quality of care, HEDIS (HEDIS, 2018), as well as substance dependence or patients who are in treatment for substance related disorders at the time of recruitment. The exclusion criteria are based on the fact that the presence of these disorders may result in divergent treatment practices compared to unipolar depression in the absence of these conditions. Our primary outcome, treatment initiation, is conceptualized as a combination of service encounters with specialty mental health (psychologists, psychiatrists) or primary care providers charted into the patients' VHA medical records (excluding assessments) that were associated with any depressive disorder diagnosis. Our data are already IRB exempt, R&D and DART approved, and have already been extracted.

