**Data processing.** Data will be initially checked for out of range values and missing data where appropriate through plotting and descriptive analyses. Data will be transformed as needed. Logistic regression is relatively free of restrictions and can accommodate a mix of predictors (continuous, discrete, dichotomous) (Tabachnick & Fidell, 2007). *With continuous predictors, the assumption is that there is a monotonic relationship (increase or decrease) between the predictor variable and odds of the binary outcome (i.e. engagement or lack of engagement in care). The functional of this linear assumption can be evaluated by use categorical indicator variables as well as transformations of the continuous variable, such as a quadratic form. Multicollinearity will be tested using two approaches. First, we will explore correlations among IVs and exclude variables based on high correlations ( $> .65$ ). Second, we will examine the size of the standard error (SEs) relative to the beta coefficient for each predictor in the model. Large SEs will be indicative of potential multicollinearity. Residuals will be tested to identify possible outliers.*

Analysis plan:

**Modeling risk for lack of treatment engagement.** For all analyses, lack of treatment engagement is the main dependent variable and will be investigated using three related definitions based on the date in which a PHQ9 score  $\geq 10$  is identified in the EHR. Specifically, we will examine whether treatment is initiated within 3-months, 6-months, or 12-months from the date of the PHQ9 assessment. *Independent variables of interest will be extracted based on proposed framework, empirical evidence, and availability in the EHR (see Table 1), including insight from a select number of semi structured surveys collected prior to data analysis (described below).*

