*Fortunately, the EHR is rich in terms of wealth of potential predictors to carry out the analyses. This work is a first step in the development of an automated system that can be implemented in the VHA EHR to more easily identify patients who may be in need but at risk for lack of engagement in mental health treatment.* A direct logistic regression will be performed to evaluate the battery of proposed and potential factors as possible predictors of lack of treatment engagement. The final model will be estimated using the validation sample (half of our overall available sample). Regression (beta) coefficients and odds ratios will be extracted for interpretation and evaluation of risk to not engage in treatment in our next step.

*Computation of health service utilization risk score.* Using coefficients extracted from final logistic regression testing the best fitting patient phenotype associated with lack of treatment engagement, we will compute a risk score for lack of treatment engagement. This score will be used to select high risk patients enrolled in our intervention development and evaluation studies (Aims 2 and 3). The logistic regression equation will be used to calculate the risk scores using the intercept and co-variated specific coefficients that relate to the probability of lack of treatment initiation. Therefore, the equation will be based on the logistic regression model which will be developed in the log odds scale.

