- Potentially temporary states/situations that may significantly impair mood/capability to engage in treatment: unstable environment that is not in one's control (e.g., homeless, temporary group home, extensive care taking duties).

Sampling plan: The target population is a clinical sample of Veterans with depression who meet the criteria in Table 2. Exclusion criteria are consistent with conventional depression studies. Veterans will be excluded if they have a medical disorder that would significantly increase their risk of depression secondary to a medical diagnosis or due to treatments for those medical diagnoses (e.g., cardiovascular disease; SUD) or those experiencing side effects with standard treatment or would require a significant adaptation of treatment (e.g., bipolar disorder). Veterans will also be excluded consistent with the standard of care for cognitive and/or behavioral treatment of depression at Tampa VA (e.g., actively suicidal patients that need intensive and immediate treatment). Patients will need to have a risk score associated with lack of treatment initiation as determined in Aim 1.

Recruitment: The Tampa VA is an ideal site because it has a large and diverse mental health population. In FY17 over 2000 patients had a first visit to primary and specialty mental health care, with over half showing a depression diagnosis in their charts. Veterans will be recruited using the following methods: 1) Depression treatment consults. Veterans referred for mental health treatment (psychotherapy or medication) through the mental health consult service will be informed about the proposed CDA clinical trial either by their provider or the study RA who will regularly monitor MH referrals on CPRS. 2) Advertisement. IRB-approved brochures will be placed throughout Tampa VA (e.g., primary care, pharmacy). Interested Veterans can contact study staff to learn more about participating. 3) Referrals from providers. Tampa VA providers in primary care - mental health service lines will be informed of the study and given research brochures. Providers can then give information to Veterans referred to specialty care for treatment.

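### The Aim 1 risk score and its cut-off are set in PHQ-9-positive Veterans regardless of referral but select patients for an intervention aimed at referred Veterans, and performance among the referred is never checked

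*Protocol*

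**What the plan says.** **Where the score is built.** Protocol section A4a (study overview) states that "we plan to use the 88,456 OEF/OIF Veterans with a Patient Health Questionnaire 9 (PHQ9") of at least 10. The cohort paragraph adds that these are Veterans "who were not already in treatment for depression prior to this PHQ9 assessment" and lists excluded diagnoses. Neither place requires a referral, and Table 1 lists no referral or consult variable. For the outcome, "we will examine whether treatment is initiated within 3-months, 6-months, or 12-months from the date of the PHQ9 assessment". Table 1 defines initiation as "A primary or secondary stop code showing a visit in mental health (with a psychologist or psychiatrist) or primary care AND an ICD9 for depression".

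**How it is tuned and judged.** The development and validation split, the ROC cut-off and the machine-learning validation all use this cohort. An AUC below 0.8 is read as a sign that important variables are missing (A4a, steps to control for unobserved variables).

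**Where it is used.** A4a says "This score will be used to select high risk patients enrolled in our intervention development and evaluation studies (Aims 2 and 3"). The Aim 2 sampling plan (A4b), which Aim 3 follows, makes it a condition of entry: "Patients will need to have a risk score associated with lack of treatment initiation as determined in Aim 1". Section A2 describes the target group: "Our study focuses on solidifying engagement in care for those patients whose needs have been identified by provider and have been referred for care". The introduction to A4 places the intervention between referral and the first mental health treatment visit.

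**The concern.** A score carries its AUC and cut-off from one population to another only if the outcome means the same thing in both. Here it does not. A Veteran in the Aim 1 cohort can be a non-initiator by never being referred, by having no depression-coded primary care visit, or by being referred and not attending. In the group the intervention targets, the first of these cannot occur.

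The score may therefore owe part of its apparent discrimination to steps that referred Veterans have already passed. The cut-off is then tuned to the wrong mix of outcomes, and the 0.8 check can be passed without showing that the score ranks referred Veterans well. Selection by risk score is the stated link between Aim 1 and Aims 2 and 3, and the pilot prepares a later RCT.

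**Working it through.** The documents give no performance figure for the score and no referral or attendance rate, so there is nothing of the plan's own to reproduce. The figures below are illustrations under stated assumptions.

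**Step 1: how much non-initiation could be absence of referral?** As a simplification, suppose initiation requires referral. Let r be the proportion referred and p the overall initiation rate. The share of non-initiators who were never referred is (1 − r)/(1 − p). For p, I use 18.5% and 27%, the range in section A1 for any mental health care use among Veterans. It stands in for initiation in this cohort, which is an assumption.

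| r (assumed) | p = 18.5% | p = 27% |
|---|---|---|
| 30% | 0.70/0.815 = 86% | 0.70/0.73 = 96% |
| 50% | 0.50/0.815 = 61% | 0.50/0.73 = 68% |
| 70% | 0.30/0.815 = 37% | 0.30/0.73 = 41% |
| 90% | 0.10/0.815 = 12% | 0.10/0.73 = 14% |
| 100% | 0% | 0% |

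**Step 2: one predictor.** Let x be standard normal, with higher values meaning higher risk. Set logit P(referred) = −0.25 − 1.5x, which refers about 46%, and logit P(attend, given referred) = 0.2 − c·x. Initiation is referral and attendance together. AUC of x for non-initiation, by simulation:

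| c (attendance effect) | All Veterans | Referred only |
|---|---|---|
| 0 | 0.73 | 0.50 |
| 0.3 | 0.77 | 0.57 |
| 0.7 | 0.81 | 0.66 |
| 1.0 | 0.83 | 0.71 |
| 1.5 (equal effects) | 0.86 | 0.78 |

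The c = 0.7 row shows the practical difficulty: the full-cohort AUC passes 0.8 while the AUC among the referred is 0.66.

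**Step 3: allow initiation without referral.** Table 1 counts primary care visits. If 10% or 20% of unreferred Veterans initiate that way, with c = 0, the overall AUC falls to 0.67 or 0.62. Among the referred it stays at 0.50.

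**Step 4: a fitted score.** Take n = 88,456, split in half, with one predictor of referral and one of attendance (slope 1 each). The referral predictor's effect on attendance is set to −0.5, 0 or +0.5. Fit a logistic score on everyone and another on the referred only, and test both in referred Veterans, with p = 27%.

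| r (assumed) | Score fitted on all | Score fitted on referred |
|---|---|---|
| 30% | 0.43 to 0.65 | 0.74 to 0.78 |
| 50% | 0.63 to 0.72 | 0.74 to 0.76 |
| 70% | 0.71 to 0.75 | 0.74 to 0.76 |
| 90% | 0.74 to 0.76 | 0.74 to 0.76 |

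At r = 90% the two scores differ by at most about 0.004. At r = 50%, where 46% of the referred do not attend, the top risk quartile of referred Veterans contains 62% to 71% non-attenders under the all-cohort score and 73% to 76% under the referred-only score.

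**The case against.** Most of the case against concerns size, and much of it stands.

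- **Shared predictors.** A4a ties severity, gender and race to perceived need and openness to care, and does not mention referral. Openness plausibly still affects attendance. Table 1 also lists distance and ability to reach the VA, which bear on attendance directly. A reader might infer that the predictors stop mattering once a Veteran is referred; the documents do not support that.
- **Referral is not needed for initiation.** Primary care visits count, so Step 1 is a simplification. This stands, but it adds another component to the mixed outcome and does not remove the mixing.
- **Recruits are mostly referred already.** A4b recruits mainly through consults and provider referrals, so the score would seldom enrol unreferred Veterans. Brochures are a further route, and Table 2 has no referral criterion. The main harm is mis-ranking among the referred.
- **Benefit is wider than attendance.** The intervention includes symptom and mood monitoring aimed at perceived need, and section A1 expects self-management to help non-engaged as well as newly referred patients. It does not follow that only referred non-attenders can benefit.
- **Some input from referred non-attenders.** Ten Veterans who were referred but missed their appointment are surveyed before modelling and inform the choice of predictors. This helps, but it is not a check of performance.
- **Small stakes.** The score selects 6 patients in Aim 2 and 15 in Aim 3, for formative purposes. This limits the consequence.

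**Conclusion.** The mismatch can be read from the protocol: the score, the ROC cut-off and the 0.8 check belong to a cohort defined without referral, the score is a condition of entry to aims directed at referred Veterans, and no step checks it in them.

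The size is unknown. It depends on the referral rate and on how far the same predictors drive referral and attendance, and the documents give neither. Under the Step 2 assumptions, AUC among the referred is 0.50 to 0.78 against 0.73 to 0.86 overall. The loss is modest when effects are shared and negligible when nearly all are referred. A reader might conclude that the pilot sample would be little better than a random draw from referrals. That holds only if attendance shares almost no predictors with referral, which the documents do not say.

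This is a worthwhile, inexpensive improvement to a formative study, and it does not invalidate Aim 1 as a description of the wider population.

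**What to change.** Flag Aim 1 Veterans who had a mental health consult after the index PHQ-9. In that sub-cohort, with follow-up starting at the consult date, report the score's AUC and calibration and set the selection cut-off. If performance drops, re-estimate the score there. Use that cut-off for Aims 2 and 3, and keep the full-cohort model as the population description.

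The cost is a consult date, possibly a data-access update because A4a says the data are already extracted, and a repeat of the planned analysis in a subset. The documents do not say whether the extract holds consult data. The sub-cohort will be smaller than 88,456, and the AUC may look less favourable. In return, the sponsor learns before recruitment whether the score ranks the patients it is meant to select.

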*Machine learning process.* This step of the data analysis will be conducted to assess the extent to which machine learning methods can potentially improve upon the prediction accuracy derived from the conventional logistic regression analysis. As with the conventional logistic regression analysis, the cohort of 88,456 OEF/OIF Veterans will be used. A range of machine learning methods will be used to compare results on variable importance and interpretability, with the goal of providing insight for clinicians on potential risk mitigation strategies for veterans at risk of not engaging in treatment for depression. The methods to be compared will include Lasso penalized logistic regression (Tibshirani 1996), random decision forests (Liaw 2002), decision trees (Hastie 2009), and support vector machines (Hastie, 2001). Each approach offers potential pros and cons in terms of modeling complex data and in interpretation. For example, decision trees accommodate high dimensions, model non-linear relationships, and perform well with missing data and are highly interpretable by humans. Support vector machines provide automated scaling of predictor variables and support linear and polynomial kernels for model training. Regardless of the method used, to prevent overfitting, 10-fold cross validation will be employed. This process splits the data into ten separate sets and builds a model on each set using the other nine sets. Variance across the ten models will be examined to evaluate model stability. Model performance will be evaluated using the standard F-Measure which is the harmonic mean of precision and recall. This will be augmented with use on metrics of predictive performance including area under the curve (AUC), sensitivity, and specificity, with a focus on clinical interpretability. Error analysis will be employed to improve model performance on 10 separate samples until model performance is maximized on the test set and then validated on the final set. As models are being developed, pruning algorithms will be used to make the model more generalizable. Finally, although there are no specific guidelines or power analysis for the determination of the exact sample size needed for specific models, generally samples such as  $n > 1000$  have been found to be adequate for machine learning. Our sample for this step of the analysis will be  $N = 88,456$  and we will be using the sample to its fullest. Therefore, we propose to use 10 ( $n = \sim 7000$ ) samples as training sets to test and fine-tune our phenotype model. We will use 2 additional ( $n = \sim 9000$ ) samples to do a final model testing and finally validate the model.

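### Aim 1 compares logistic regression with machine learning on different partitions of the same cohort, with no shared hold-out and an unclear fitting sample for the logistic model

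*Protocol*

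**What the plan says.** All of this is in Protocol A4a (Aim 1); the SAP contains no Aim 1 analysis.

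- **Goal.** The Study/Design overview aims to "identify the best fitting model in terms of prediction performance and interpretation, whether by logistic regression analysis or machine learning methods". The Machine learning process paragraph says that Stage 2 is there to "assess the extent to which machine learning methods can potentially improve upon the prediction accuracy derived from the conventional logistic regression analysis".
- **Stage 1 data.** The 88,456 Veterans "will be randomly split into development and validation sub-cohorts". The overview continues: "Estimates extracted from the development sub-cohort will be used to compute risk scores", with prediction accuracy then checked in the validation sub-cohort.
- **Stage 1 final fit.** The Analysis plan says instead: "The final model will be estimated using the validation sample (half of our overall available sample").
- **Stage 2 data.** "As with the conventional logistic regression analysis, the cohort of 88,456 OEF/OIF Veterans will be used". Here it becomes ten samples of about 7,000, described as "samples as training sets to test and fine-tune our phenotype model", and two further samples of about 9,000 for final testing and validation. Ten-fold cross-validation is also to be used, each model being built from nine of the ten sets.
- **Metrics.** ROC analysis is named for Stage 1. The F-measure, supplemented by AUC, sensitivity and specificity, is named for Stage 2. Three outcome windows are planned (3, 6 and 12 months).
- **Use.** The resulting risk scores select patients for Aims 2 and 3. The risk-score paragraph computes them from logistic coefficients, although the overview leaves open which method wins.

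The protocol does not say that the stages share a hold-out set, that the Stage 2 sets are nested in the Stage 1 halves, or how the difference in accuracy will be estimated.

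**The concern.** To attribute a difference in accuracy to the method, the other conditions should be the same. Here two others change with the method: the number of people who train the model and the people on whom it is scored. The machine-learning training size is itself ambiguous, since the text supports either about 7,000 or nine times that.

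The conflict over the logistic fit adds an asymmetry. If the final logistic model is estimated in the validation half, no stated half remains to measure its accuracy independently, while machine learning keeps a final set. If the overview is followed, both methods have held-out data.

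At stake are the main methodological conclusion of Aim 1 and, possibly, the score used to recruit for Aims 2 and 3.

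**Working it through.** **1. The plan's own partition.** 10 × 7,000 + 2 × 9,000 = 88,000, against 88,456. The shortfall of 456 (0.5%) is rounding, so the figure reproduces. The Stage 1 halves are 88,456 / 2 = 44,228.

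**2. What differs between the methods.**

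| | Logistic regression | Machine learning |
|---|---|---|
| Training size | 44,228 | about 7,000, or 9 × 7,000 = 63,000 |
| Final evaluation set | 44,228 (overview); no independent half (Analysis plan) | about 9,000 |

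**3. Size of the training-size effect.** This comes from a small simulation: 6 replicates per setting, 30, 60 or 100 normal predictors, logistic models only. The table shows the mean AUC loss against the true model.

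| Predictors | Trained on 7,000 | Trained on 44,228 | Difference |
|---|---|---|---|
| 30 | 0.0033 | 0.0005 | 0.0028 |
| 60 | 0.0053 | 0.0010 | 0.0043 |
| 100 | 0.0103 | 0.0017 | 0.0086 |

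Training size alone can therefore move AUC by up to about 0.01. Scoring a logistic model on the same 44,228 people who fitted it inflated AUC by at most 0.0036. Flexible learners were not simulated.

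**4. Precision of the AUC difference.** The documents give neither the AUC nor the outcome rate for this cohort. Assumptions:

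- AUC 0.65-0.80; the upper end is the benchmark in the paragraph on unobserved variables.
- Non-engagement p = 73-81.5%, the complement of the 18.5-27% utilization in section A1. That figure describes Veterans generally, not this PHQ9 ≥ 10 cohort.
- Correlation r between the two methods' AUC estimates on the same patients: 0.70-0.95.

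Hanley-McNeil, with A the AUC, n1 = np, n2 = n(1 − p), Q1 = A/(2 − A) and Q2 = 2A²/(1 + A):

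SE² = [A(1 − A) + (n1 − 1)(Q1 − A²) + (n2 − 1)(Q2 − A²)] / (n1·n2)

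Example with A = 0.65, p = 0.815, n = 9,000: n1 = 7,335, n2 = 1,665, Q1 = 0.4815, Q2 = 0.5121, A² = 0.4225.
SE² = (0.2275 + 432.57 + 149.13) / 12,212,775 = 0.00004765, so SE = 0.0069. At n = 44,228 the same inputs give SE = 0.0031.

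- Separate sets: 1.96 × √(0.0069² + 0.0031²) = 0.0148.
- Shared 9,000: 1.96 × 0.0069 × √(2(1 − r)) = 0.0105, 0.0086, 0.0061 and 0.0043 at r = 0.70, 0.80, 0.90 and 0.95.

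At the other corner (A = 0.80, p = 0.73) the SEs are 0.00467 and 0.00211. Separate sets give 0.0100; a shared 9,000 gives 0.0071, 0.0058, 0.0041 and 0.0029.

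| Design | 95% half-width for the AUC difference |
|---|---|
| Separate sets, 9,000 against 44,228 | 0.010-0.015 |
| Shared 9,000, r = 0.70-0.80 | 0.006-0.0105 |
| Shared 9,000, r = 0.90-0.95 | 0.003-0.006 |

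**5. Overlap, if the two splits are drawn independently (not stated).** About 70,000 / 2 = 35,000 of the 44,228 in the logistic validation half (79%) would be machine-learning training data. About 9,000 / 2 = 4,500 of the machine-learning final set would lie in the logistic development half. Only about 4,500 people would be in both final evaluation sets.

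**The case against.** **Each method is still validated on its own terms.** Random subsets of one cohort estimate the same population accuracy, so overlap between the two partitions does not bias either method's own held-out estimate. This stands. A reader might infer from the 79% overlap that results will be contaminated. That would require scoring one method on the other's hold-out, which the protocol does not plan, and the overlap figures also assume independently drawn splits.

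**The planned precision is adequate.** A half-width of 0.010-0.015 is good enough for most model choices. This largely stands: it is tempting to call the comparison imprecise, and the figures do not support that. Nor does a shared set guarantee that very small gains can be seen. A true gain of 0.005 is beyond the half-width throughout the assumed range only when r is near 0.95, and that correlation has no source in the documents.

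**Stage 2 already includes a logistic model.** Lasso-penalized logistic regression is among the Stage 2 methods and can be compared with forests, trees and support vector machines on shared patients. This helps only in part, because the stated comparator is the conventional logistic model from Stage 1.

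**The consequences are small.** Selection also weighs interpretation, and the score recruits only 6 patients in Aim 2 and 15 in Aim 3, where a shift of 0.01 AUC would hardly change enrolment. That is fair for recruitment. It does not answer the point for Aim 1, whose stated goal is the comparison itself.

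**Conclusion.** The point holds as a weakness of the comparison. The plan makes the choice between two approaches a goal, then gives them different training sizes and test patients, with no shared hold-out and no paired estimate. The likely confounding is modest, about 0.01 AUC or less, on a small simulation confined to logistic models. A shared set matters only for true differences of about 0.015 or less, under the assumed AUC, outcome rate and correlation.

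The contradiction over the final logistic fit needs no assumption: the overview and the Analysis plan cannot both be followed. Taken literally, the Analysis plan leaves the logistic model without an independent half.

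A reader might go further and conclude that the validation results are biased or the comparison is too imprecise to use. The documents support neither. This should be corrected before modelling, but it does not threaten the rest of the study.

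**What to change.** 1. Before any modelling, save one seeded partition for both stages, using the Stage 2 sizes: about 70,000 for development, about 9,000 for model choice and about 9,000 locked for the final test.
2. Run 10-fold cross-validation in the development set for every method, including conventional logistic regression, and state the resulting training size.
3. Score all models on the same patients, with the same metrics and outcome window. Report the paired AUC difference with its 95% confidence interval (DeLong or bootstrap).
4. Reconcile the Study/Design overview with the Analysis plan, so that the logistic model is fitted in development data only.
5. State that the chosen model, logistic or not, supplies the risk score for Aims 2 and 3.

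**Cost.** Protocol wording and one split file; no new data. The logistic model would be validated on about 9,000 people instead of 44,228. Under the same assumptions, the 95% half-width for its own AUC (1.96 × SE) widens from about 0.004-0.006 to about 0.009-0.014.
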